ITT	Intention-to-treat = including all data from all subjects who have participated in the clinical investigation
MDCG	Medical Device Coordination Group
PMCF	Post-Market Clinical Follow Up
PP	Per Protocol analysis = including only data from subjects who have completed the clinical investigation completely in accordance with the CIP, with no deviations from the CIP
RFA	Radiofrequency ablation
SADE	Serious Adverse Device Effect
SAE	Serious Adverse Event
USADE	Unanticipated Serious Adverse Device Effect
VAS	Visual analog scale

Clinical Investigation Plan
 Study Code: ES-100
 CIV-ID: CIV-23-06-043373

1. Synopsis

Background and rationale:	
Investigational device:	EndoSign® Cell collection device
Number of subjects:	75 (15 per site)
Inclusion criteria:	
 ● Patients with histopathologically confirmed diagnosis (intestinal metaplasia) of Barrett's oesophagus (BE) and at least COM1 ● Active monitoring with planned surveillance endoscopy within 3 to 12 months ● Age: 18 – 84 years
Exclusion criteria:	
 ● Scheduled for other endoscopic treatment (e.g. ablation) at the next surveillance endoscopy ● Alarm symptoms 
 ○ Dysphagia and/or food sticking ○ Dyspepsia and weight loss ○ Dyspepsia and anaemia ● Patient with a diagnosis of an oropharyngeal, oesophageal or gastro-oesophageal tumour ● Patient who has had treatment to the oesophagus e.g. endoscopic mucosal resection, endoscopic submucosal dissection, radio frequency ablation, surgery within the previous two months ● Patient known to have gastric or oesophageal varices or cirrhosis of the liver ● Patient with a known anomaly of the oesophagus e.g. webbing, pouch, stricture etc ● Patients unable to give consent ● Patients who have had a stroke or any other neurological disorder where their swallowing has been affected ● Patients who have had a myocardial infarction in the last 3 months ● Patients who have had fundoplication or other surgery to oesophagus and proximal stomach ● Patients using anti-trombotic drugs which cannot be temporarily discontinued

Clinical Investigation Plan
 Study Code: ES-100
 CIV-ID: CIV-23-06-043373

[figure not shown]
Study objectives:	
 • To determine whether it is feasible to use EndoSign® Cell collection device in patients with Barrett's oesophagus under surveillance • Acquire data and experience to assess whether it is possible to perform a full scale study in the future and identify what design modifications are needed • Determine steps necessary for implementation in secondary care.
Study endpoints:	
 • Acceptability • Safety • Assess the feasibility of recruitment • Implementation in secondary care • Data collection method and outcome measures • Preliminary evaluation of histopathological results
Planned duration of the clinical investigation:	Q4 2023 – Q3 2024

2. Identification and description of the investigational device

2.1. Description of the investigational device

EndoSign® Cell collection device is a CE-marked non-endoscopic cell collection device used to detect Barrett's oesophagus, early cancer and other oesophageal conditions. It consists of a tethered sponge in a gelatine capsule attached to a string that is swallowed and when removed from the stomach, it collects cells along its way. The sample is then put into a preservative which is stable at room temperature. It is processed in a central laboratory and can be assessed for Barrett's biomarker Trefoil Factor 3 (TFF3), atypia and will be stained for p53 as an indicator for dysplasia or cancer.

Clinical Investigation Plan
Study Code: ES-100
CIV-ID: CIV-23-06-043373

2.2. Intended purpose

The EndoSign® cell collection device is to be used for the collection of cells from the surface of the oesophagus for molecular, cytological, and histological analyses.

The investigational device is CE marked and will be used according to its intended purpose in this clinical investigation.

2.4. Model/type

Generic denomination: Cell Collection Device

Device name: EndoSign® Cell collection device

Device trade name: ES-CYT-102

Model: Not applicable

Medical device classification: Class I

European Medical Device nomenclature: A99 (Devices for administration, withdrawal and collection- other)

2.5. Target population

Target Population: Patient's aged 18 and over

Version No: 1.1
Date: 2023-11-29

Clinical Investigation Plan
Study Code: ES-100
CIV-ID: CIV-23-06-043373

Intended User Group: The EndoSign® Cell collection device is to be administered by trained healthcare professionals such as medical doctors, registered nurses, and other qualified health professionals trained in use of the device

2.6. Detailed description of the investigational device and materials coming into contact with the human body

See Appendix A – EndoSign® Cell collection device instruction manual

2.7. Medical or surgical procedures

See Appendix A – EndoSign® Cell collection device instruction manual

2.8. Summary of required training/experience needed

Any personnel administering the EndoSign® will undergo a training webinar and in person training until they are signed off as competent (usually 8-10 procedures).

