2.10. Rationale of study

When it comes to surveillance of Barrett's oesophagus, there is a need to enhance the clinical pathway and streamline the use of resources. There is also a reason to evaluate and introduce alternative surveillance methods that are better tolerated by patients. Cell collection device with sponge can be one such method, EndoSign® has not yet been used in Swedish healthcare and the method therefore needs to be evaluated in our setting. The similar cell collection device Cytosponge have been used as a triage tool, patients under surveillance could be divided into various risk groups. This might direct medical interventions toward people who are most at risk of developing cancer. In the future, Cell

Clinical Investigation Plan
Study Code: ES-100
CIV-ID: CIV-23-06-043373

collection device with sponge might be used to screen patients with gastroesophageal reflux disease (GERD) for Barrett's oesophagus.

In order to be able to conduct high-quality research on Barrett's oesophagus, a sufficiently large patient base is needed. Both regional and county hospitals conduct surveillance, so it would be advantageous if they all collaborated in future research on Barrett's oesophagus in Sweden.

With this feasibility study, it is possible to introduce and assess EndoSign® within the Swedish Barrett network at a number of hospitals in a controlled manner, which can serve as a crucial foundation for carrying out larger multi-center studies in the future.

3. Risks and clinical benefits of the investigational device and clinical investigation

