4.2. Objectives and endpoints

Objective	Endpoint	
To assess patient acceptability for EndoSign®	i. EndoSign® test experience compared to upper GI endoscopy ii. EndoSign® swallowing failures iii. Willingness to undergo EndoSign® again	i. Adapted ENDOPREM and a visual analog scale to rate experience ii. Number of patients that are unable to swallow and attempts made iii. Questionnaire
To assess safety of EndoSign® in secondary care	i. Rates of adverse events up to 7 days after EndoSign® test	i. All adverse events reported during procedure, ER-visits and 7-day follow up.
To assess the feasibility of recruitment	i. Proportion of eligible patients who participate ii. Quantify the number of patients that potentially can be recruited	i. Patients accepting invite and consent divided by total of patients invited ii. Number of patients in surveillance per site
To assess the implementation of EndoSign®	i. Costs and resources required to introduce EndoSign® in secondary care ii. Determine technology and equipment needs and training iii. Clinical staff experience and acceptability of EndoSign® in regards of training, skills, reliability, side effects and user information	i. Interviews with staff and healthcare professionals ii. Equipment needed per session iii. Number of sessions needed until fully trained. iii. Interview with clinical staff iv. Number of days from samples are sent to laboratory in UK until test results arrive

Clinical Investigation Plan
 Study Code: ES-100
 CIV-ID: CIV-23-06-043373

	iv. Logistics of TFF3-analysis of EndoSign® and response times	
To evaluate data collection method and outcome measures	i. Feasibility of questionnaires ii. Response rate for questionnaires iii. Withdrawal and drop-out rates iv. Follow-up rates	i. Validate adapted ENDOPREM ii. The proportion of patients who completes each questionnaire iii. The proportion of patients who, for various reasons, do not complete the study iv. The proportion of patients who complete the follow-up

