5.1. General information

This clinical investigation is designed as a single-armed multi-center feasibility study and is expected to be conducted 2023/2024. The aim is to include 15 consecutive patients per site (75 patients in total) attending routine endoscopy in Barrett's esophagus surveillance.

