5.5. Description of the clinical procedures and diagnostic methods relating to the clinical investigation

EndoSign® test procedure

Study patients are referred to a separate visit to undergo the EndoSign® test. They will be required to refrain from food and liquids for 3–4 hours before the visit and they will respond to a socio-demographic- and clinical form and assessment of symptoms and EQ-5D.

Clinical Investigation Plan
Study Code: ES-100
CIV-ID: CIV-23-06-043373

The EndoSign® is administered by a nurse or healthcare professional that has undergone adequate procedure training. The procedure time is 7 minutes with an overall clinic session taking about 20- 30minutes in total.

The patient is asked to swallow the EndoSign® capsule together with some water. The end of the suture is attached to an applicator which the nurse hands to the patient to hold. The capsule will be in the patient's stomach for around 7minutes until it dissolves completely, allowing the sponge to expand to its full size. The sponge is withdrawn by the nurse using the suture. The patient can choose to get local anaesthetic spray into their throat before the sponge is removed. The sponge is then placed in a sample collection kit provided by Cyted and secured with a patient number identification label.

The patient will be instructed to try again if they are unable to swallow the capsule the first time. Before being labelled as "EndoSign® swallowing failure," patients will have a maximum of two failed attempts.

After 30 minutes, patients are asked to answer forms about anxiety level and procedure-specific questions to evaluate acceptability. The visual analog scale (VAS) and a quick questionnaire using the adapted ENDOPREM measure will be used.

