8.1 Case Report Form

All data will be anonymized and stored in an electronic study database (e-CRF) using REDCap. The following data will be collected and reported directly in the CRF:

- Sex, age, BMI
- Smoking / Alcohol consumption
- Use of PPI or other acid suppressants
- Year of diagnosis
- Prague classification according to previous endoscopy
- Previous dysplasia
- Previous endoscopic treatments
- Patient-reported experience measurement data (ENDOPREM, VAS)
- Questionnaire results (including EQ-5D)
- EndoSign® -TFF3 test results
- Gastroscopy results (including biopsy results)
- Adverse events

Both written and electronic changes or corrections on CRF will be dated, initialed and explained (if necessary)

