The investigational device(s) will only be used in the clinical investigation and according to the clinical investigation plan. The sponsor provides the site with written instructions and technical support.

The investigator will keep records to document the physical location of all investigational devices from shipment to return/disposal. This record should include: name(s) of clinical investigation personnel who received, used, returned, or disposed the device, the date of receipt, identification and quantity of each investigational device (batch number/serial number or unique code), the expiry date, the date or dates of use, subject study-ID, date on which the investigational device was returned, the date of return of unused, expired or malfunctioning investigational devices, and the date and documentation of disposal of the investigational devices as per instructions of the sponsor.

12 Statements of compliance

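### Are the 8-10 sign-off procedures per operator done on study patients, and does it matter that the protocol does not say?

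*Protocol*

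**What the plan says.** Section 2.8 requires a webinar and then "in person training until they are signed off as competent (usually 8-10 procedures"). Section 5.5 (EndoSign test procedure) says the study test is "administered by a nurse or healthcare professional that has undergone adequate procedure training", and section 2.5 likewise describes the users as trained professionals.

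Section 2.10 states that the device "has not yet been used in Swedish healthcare and the method therefore needs to be evaluated in our setting". Section 2.9 adds that it is CE-marked and already in routine use in the English health service.

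Section 5.1 sets the size: "The aim is to include 15 consecutive patients per site (75 patients in total"). Section 4.2 lists, among the implementation measures, "Number of sessions needed until fully trained".

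Section 11 says "The investigational device(s) will only be used in the clinical investigation and according to the clinical investigation plan" and asks the investigator to keep a device record that includes "name(s) of clinical investigation personnel who received, used, returned, or disposed the device", the dates of use and the subject's study ID. Section 8.1 introduces its list with "The following data will be collected and reported directly in the CRF". That list has no item for operator or sign-off status.

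**The concern.** Eight to ten procedures is a large number beside 15 patients per site. The device is new to Sweden, so no pool of experienced local operators can be assumed, and counting sessions to full training as a study measure suggests that training happens during the study. If operators qualify on study patients, section 5.5 would not describe the early tests. If they qualify locally on other patients with study devices, section 11 seems to forbid it.

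Swallowing failures, inadequate samples and adverse events to 7 days are meant to inform a full-scale study. If they mix trainees with signed-off staff and nothing marks which is which, a planner could not tell whose performance the rates describe. With sign-off status missing from the CRF list, it may also look as though no later analysis could separate the two.

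**Working it through.** **Inputs.** Sign-off at 8 to 10 procedures per operator (section 2.8). 15 patients per site and 75 in total (section 5.1), so 75/15 = 5 sites, and 5 x 15 = 75 reproduces the stated size. Section 7.1 gives no power calculation, so there is none to check. Operators per site and procedures done before enrolment (k) are not given. Both are assumptions, varied below.

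**Share of tests before sign-off, if training is on study patients.**

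- One operator per site, max(0, need - k)/15 with need = 8 or 10:
  - k = 0: 8/15 = 53% to 10/15 = 67%. Over 5 sites, 40 to 50 of 75, leaving 35 to 25 after sign-off.
  - k = 4: 4/15 = 27% to 6/15 = 40%.
  - k = 8: 0 to 2/15 = 13%.
  - k = 10: 0%.
- Two operators splitting the 15 as 8 and 7, [min(8, need - k) + min(7, need - k)]/15, each term not below 0:
  - k = 0: 15/15 = 100%.
  - k = 4: 8/15 = 53% to 12/15 = 80%.
  - k = 8: 0 to 4/15 = 27%.
  - k = 10: 0%.

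Taken as written, section 5.5 corresponds to 0%.

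**What a mixture could do.** The documents give no learning effect. With purely assumed swallowing failure rates of 20% before sign-off and 10% after, the pooled rate would be (40 x 0.20 + 35 x 0.10)/75 = 11.5/75 = 15.3%, or (50 x 0.20 + 25 x 0.10)/75 = 12.5/75 = 16.7%. With equal rates it is 10% whatever the mixture.

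**What a split could show.** The exact 95% upper limit with zero events is 1 - 0.025^(1/n): 4.8% for n = 75, 10.0% for n = 35 and 13.7% for n = 25. A split would be descriptive only.

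**Do the passages exclude one another?**

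- Sections 2.5 and 5.5 say operators are trained. Sign-off before the first study test satisfies both, and also section 2.8.
- Section 11 confines study devices to use in the investigation and under the plan. Section 2.8 is part of that plan, so training that it prescribes is arguably covered. Training on other CE-marked stock, or where the device is already routine, would not touch section 11 at all.
- Lack of prior Swedish use (section 2.10) limits local experience but does not rule out training elsewhere.
- The session count in section 4.2 can be kept whether training comes before or during enrolment.

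**Can experience at each test be recovered?** The section 11 record gives user, date and subject, so each operator's study tests can be put in order. Section 4.2 supplies sessions to full training. Together they largely give status at each test, provided sessions are counted per operator and can be matched to procedures. The section 8.1 list is not a full inventory: it also omits swallowing attempts, laboratory turnaround and staff interviews, all of which section 4.2 commits to measuring. Absence from it does not show that an item goes unrecorded.

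**The case for a change.** The strongest case for a change is that who performs the test, and on whom they learn, belongs in the protocol; an analysis plan cannot settle it afterwards. One sentence would do so, and the share at stake could be most of the sample. The readings that reconcile the passages (training abroad, other stock, training counted as use under the plan) are inferences that no section states. Rebuilding sign-off status also depends on how sessions are counted, and sessions need not equal procedures.

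Part of this stands. The available text does not say where the sign-off procedures are done, and sign-off status at each test is not a named data item. Appendix A and some protocol pages are not available, so the silence is established only for the text at hand.

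The step from silence to harm does not stand. No bias is shown, and the large shares arise only from assumed numbers of operators and assumed prior practice. If early-operator tests are included, they are part of what the study sets out to observe: introducing the device in a new setting, with training and staff experience among its measures. Section 7.1 says accuracy and effectiveness are not evaluated. Section 4.2 names measures without ruling out breakdowns, so tabulating them by operator experience remains open to the analysis plan.

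**Conclusion.** No change is needed. This is an unstated detail, not a contradiction. Followed as written, the plan yields either 75 tests by signed-off staff or a mixture that is legitimate for a feasibility study with training among its endpoints. The share before sign-off could lie anywhere from 0% to 100%, but that span comes from two quantities the documents do not give, and its effect on any rate is unknown.

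A sentence in section 2.8 would spare readers the question, but the pooled results would remain the main ones. An analyst who wants to show experience can order the tests from the device record and use the session count.

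The conclusion assumes that the section 11 record is kept as described and that training sessions are counted per operator. If neither were done, status could not be rebuilt, but that would be a failure to follow the plan, not a fault in it.

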2.9. Background

The incidence of esophageal adenocarcinoma has increased dramatically in the Western world in recent decades [1]. Barrett's oesophagus is a premalignant condition with an approximately 0.3% annual risk of developing into adenocarcinoma[2]. Globally, Esophageal squamous cell carcinoma (ESCC) still accounts for 90% of new cases of esophageal cancer[3], but in Sweden, adenocarcinoma is more common.

Symptomatic oesophageal cancer has a poor prognosis as the disease is often detected in late stages. However, the prognosis for early/superficial cancer is very good.

According to epidemiological studies the prevalence of Barrett's oesophagus is between 0,5 - 2%. [4] Less than 10% of patients resected for adenocarcinoma have previously been diagnosed with Barrett's oesophagus[5] and therefore in most cases of esophageal adenocarcinoma there has been no way to prevent progress.

There are now good endoscopic treatments for dysplasia and early cancer, such as endoscopic mucosal resection (EMR), endoscopic submucosal dissection (ESD) and radiofrequency ablation (RFA).

Patients diagnosed with Barrett's oesophagus are usually included in a surveillance program according to European guidelines [6]. Surveillance intervals are stratified according to BE lengths. Studies have shown that surveillance leads to earlier detection of cancer and improved survival[7, 8]. Endoscopic surveillance is an invasive method with high costs. Some patients have difficulty tolerating upper GI endoscopy, which can therefore lead to discomfort, stress and anxiety.[9]. There is a reason to believe that the number of surveillance endoscopies in patients at low-risk of developing cancer can be reduced. On the other hand, high-risk patients should undergo intensified follow-up and treatment in tertiary referral centers.

There is currently no evidence that general screening for BE lowers mortality in EAC and endoscopic screening for Barrett's oesophagus is only considered in high risk groups. [6, 10]

Version No: 1.1
Date: 2023-11-29

Clinical Investigation Plan
Study Code: ES-100
CIV-ID: CIV-23-06-043373

The EndoSign® is a CE-marked non-endoscopic cell collection primarily used for the detection of Barrett's oesophagus, early cancer, and other oesophageal conditions such as eosinophilic esophagitis. The device is composed of a tethered sponge housed within a HPMC capsule, which is connected to a string for easy retrieval.

When swallowed and subsequently pulled out of the stomach, it gathers cell samples along its path. These samples are then preserved in a room temperature stable medium. They are subsequently sent to a central laboratory for processing and can be analysed for Barrett's biomarker Trefoil Factor 3 (TFF3), atypia, and stained for p53, which serves as an indicator for dysplasia or cancer.

The EndoSign®'s cell collection, sample processing, and analysis capabilities parallel those of the previously used Cytosponge. Cytosponge-TFF3 test has been shown to detect Barrett's oesophagus effectively. A review of 5 studies underscored the safety and high patient acceptability of this procedure [11]. Remarkably, over 90% of patients succeed in swallowing the Cytosponge on the first try with no serious adverse events reported to date. The risk of detachment is minimal, being less than 1:5,000, and the most common side effect is a sore throat.

Iqbal et al showed in a systematic review that Cytosponge-TFF3 detects Barrett's oesophagus with a sensitivity and specificity of 81% and 91%, respectively. [12]

EndoSign® is a new cell collection device was recently introduced and is currently being evaluated in the Cytoprime 2 project. Based on the equivalency claims to the Cytosponge™ (see Appendix B), the device has been adopted for routine use by National Health Services, England. The EndoSign capsule sponge is:

- Simple for practitioners to use, streamlining training and clinic delivery
- Quick to administer, reducing the time taken for the procedure
- Designed to be easy to swallow, improving patient experience
- Affordable with a cost reduction per unit compared to Cytosponge™
- Safe during withdrawal due to validated and improved mechanical properties of the thread attachment.

